## Behaviour change and mediating variables

Plaque coverage provides an objective measure of tooth cleaning behaviour in the 48 hours preceding the measurement (because QLF images capture the maturity of the plaque), although it is not known whether consistent toothbrushing can be inferred. Plaque scores derived from the QLF analysis will be compared to the self-reported toothcleaning behaviour to assess the correlation between the two methods.

Differential reported behaviour change between the conditions will be assessed by creating a change score from one observation to the next by subtracting baseline scores from followup scores and conducting an analysis of mean differences using the baseline score as a covariate (Weinstein, 2007). Unless abnormally distributed, tooth cleaning behaviour will be treated as a continuum. Predicting oral health behaviours will involve the use of EPPM variables assessed during V1, and partly at V2 to predict later behavioural change.

The intervention is performed at the first visit. Thus, the change in EPPM scores (susceptibility to risk) from V1 to V2 will be used as the primary predictor variable. This will be used to predict changes in oral health behaviour from V2 to V3. We shall also use V1-V2 change scores to predict oral health behaviour changes from V2 to 6-month and 12-month (telephone) follow-ups. Structural equation models will be developed to represent these predictions, testing the predicted model as the model of best fit. Full information maximum likelihood methods (FIML) will be used to account for missing data (Muthén & Muthén, 1998–2010). With sample sizes greater than 250 participants, TLI, RMSEA, and SRMR are recommended. A TLI of .95, RMSEA of .06, and SRMR of .09 are recommended as cutoff values to accept the model as a good fit (Hu & Bentler, 1999).

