## Consent, confidentiality and anonymity

All participants in the study will receive a written information sheet relating to their aspect of the study, and a written, signed consent obtained, before their involvement in the study. All participants will be free to decline any further involvement in the study at any point. Records identifying participants will use a system of ID numbers, with no names associated with data. Data related to the views of individual patients will not be divulged to members of the dental team caring for patients, and vice versa.

#### Phase 1

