# Visit 2 (V2):

At the second visit (scheduled 2-3 weeks later), but before seeing the dentist or other dental team member, self-reported data will be collected on: self-assessed oral health data and oral health behaviours in the areas listed on the message card (given at the first visit) using an item stem of 'Since my last appointment I have..'. This will be followed by questions oral hygiene, diet and smoking behaviours as repeated measures from Visit 1. A set of EPPM items related to perceived susceptibility to risk of negative oral health outcomes will also be repeated.

A second QLF will be taken for all patients (none of these will be given to patients – they will be used to measure clinical outcomes).

At this appointment dentists or other team members will take another BPE score.

Visit 3 (V3): (scheduled 2-3 weeks after visit 2 (V2)), Self–assessed oral health and selfreported behaviour data collected on V2 will be repeated and a third QLF photograph taken to provide clinical (objectively verified data) on behaviour change.

At this appointment dentists or other team members will take another BPE score.

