# Telephone follow up (F1, F2):

There will be a telephone follow up interview of all 400 patients 6 months and 12 months after V1 to gather further data on behaviour change outcomes (self-assessed oral health and oral health) in order to give a longer term measure of change in behaviour.

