# 3. Oral health behaviours - collected at V1, V2, V3, F1, F2

There is no generally recognised measure of oral health behaviour, with individual studies using measures suited to their research questions and population characteristics. We therefore derived our set of measures for a number of sources.

- a) Questions on diet: were adapted from the National Diet and Nutrition Survey (Walker et al, 2000): 'How often, on average do you eat or drink these things?' (with response in a seven point scale from more than once a day to never); and the Adult Dental Health Survey, 2009 (Health and Social Care Information Centre, 2011): 'Do you usually have sugar (not artificial sweetener) in hot drinks like tea and coffee?'.
- b) One question on oral hygiene behaviour was taken from the Adult Dental Health Survey, 2009 (Health and Social Care Information Centre, 2011): *How often do you brush your teeth nowadays?*, with responses 1=More than twice a day, 2=Twice a

day, 3=Once a day, 4=Less than once a day, 5=Never. This was supplemented with two items adapted from the Index of Oral Hygiene Behaviour (Buunk-Werkhoven et al, 2011): '*How long do you clean your teeth for nowadays*? (with responses 1=longer than 3 minutes, 2= 3 minutes, 3= 2 minutes, 4= 1minute, 5= shorter than 1 minute), and '*How often do you do interdental cleaning*? (e.g. with floss, interdental *brushes, tooth sticks etc*).' with responses 1=At least once a day, 2=At least twice a week, 3=Weekly, 4=Monthly, 5=Never.

- c) Questions on tobacco use were derived from the World Health Organisation (2011) Global Tobacco Surveillance system.
- 4. Intention to Change Behaviour collected at V1

We will assess intentions to change target behaviours using a stem question: 'Before my next appointment I intend to..' using a five point Likert scale 1= Absolutely disagree to 5 = Absolutely agree.

- 5. Risk perception and behaviour change mediators collected at V1, V2 (perceived susceptibility to risk)
  - a) The approach: the Extended Parallel Process Model (EPPM)

Whilst the focus of the study is valuation of information, a secondary aim is to investigate whether patients' information valuation is linked to their intention to change behaviour and any actual behaviour change.

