## Comparing clinical outcomes between the three intervention arms

Comparison of QLF outcomes between the three groups will use a repeated measures mixed model approach. These models allow for analysis of multiple measurements within each participant. In this case each QLF outcome will be measured at three time-points. The first time-point is the baseline measurement, and the measurement taken here will be used as a covariate in the final model. The repeated measures approach allows us to analyse both follow-up measures (V2 and V3) together, while adjusting for the correlation of repeated measurements within participants. Using a mixed model approach, rather than a repeated measures ANOVA, allows for flexibility in the event of missing data, and can adjust for multiple covariates in the model. If there is a high level of missing data, a multiple imputation approach will be used to assess the robustness of the results. Using all the data which is available, 5 complete case data sets will be imputed, and each analysed in the same way. The results can then be combined, and compared with the analysis excluding missing data, to assess whether this would be likely to change the overall conclusions.

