## The cost-benefit framework analysis

The valuation data will be most meaningful if compared to costs. Although a cost-benefit analysis would be the ideal way of combining costs and benefits in a meaningful way, a robust cost benefit analysis of oral health risk information would entail modelling changes in disease levels resulting from behaviour change linked to the information given. In turn, it would be important to understand the lifetime (or certainly long term) consequences in terms of costs and benefits of changing disease levels. This would result in a hugely complex model, for which we have very little (and in many areas, no) evidence or data. Such a robust full scale cost-benefit analysis is therefore impossible not possible. We therefore propose to undertake a more limited outline cost-benefit framework analysis.

Thus WTP data will be combined with a cost-benefit framework analysis. The principal outcome of any such analysis would be net benefit or cost in monetary terms (i.e. £). Given that cost-benefit analysis expresses both costs and benefits in commensurate units the decision rule for cost-benefit analysis is therefore relatively simple. If the benefits (measured in £ via WTP) exceed the costs (also measured in £) this represents a gain in welfare and the strategy deemed worthwhile (Drummond et al., 1997). The level of complexity of this analysis will depend on the data available in the literature concerning longer term effects of

risk information and oral health behaviour change on oral health. The cost-benefit framework analysis will also give an indication of the likely effect of any sustained behaviour change. Data from the endpoint of the study (12 months) will be used to illustrate the effect of the behaviour change resulting for the different interventions at this time point. Results will be presented as incremental net benefits (net benefits = mean WTP – mean cost of intervention).

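### The between-arm comparison of reported behaviour to 12 months rests on ambiguously defined change scores with no missing-data method, while the drop-out-tolerant mixed model is given only to the 4-6 week QLF outcomes

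*Protocol*

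**What the plan says.** All locations are in the Protocol.

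- **Collection.** The Measures section lists "Oral health behaviours - collected at V1, V2, V3, F1, F2". F1 and F2 are telephone contacts: "There will be a telephone follow up interview of all 400 patients 6 months and 12 months after V1". Under Consent, confidentiality and anonymity, "All participants will be free to decline any further involvement in the study at any point".
- **Arm comparison of reported behaviour** (Behaviour change and mediating variables). It is made by "creating a change score from one observation to the next by subtracting baseline scores from followup scores" and then "conducting an analysis of mean differences using the baseline score as a covariate".
- **Missing data in that section.** FIML is named in a later paragraph, with the structural equation models that use V1-V2 change in perceived susceptibility to predict later behaviour.
- **Arm comparison of QLF outcomes** (Comparing clinical outcomes between the three intervention arms). This uses a repeated-measures mixed model for V2 and V3 with baseline as covariate, chosen because it "allows for flexibility in the event of missing data, and can adjust for multiple covariates in the model". Multiple imputation is added as a robustness check if much is missing.
- **Use of the 12-month data** (The cost-benefit framework analysis). "Data from the endpoint of the study (12 months) will be used to illustrate the effect of the behaviour change".

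**The concern.** The protocol recognises that visits will be missed and names a suitable remedy. It applies that remedy to the outcomes followed for 4-6 weeks and not to the one followed for 12 months by telephone, where more loss is to be expected. A pairwise change score ignores what is known from the visits that a patient did attend before leaving. If patients who have not changed their behaviour are more likely to stop answering, and this differs by arm, the comparison among those still answering can favour an arm because its less successful patients have gone. Patients know which form of information they received, so a difference between arms is plausible, though nothing in the protocol establishes it.

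The defining sentence is also unclear. Its first half describes steps between consecutive visits and its second half describes change from baseline. These are different estimands and they lose different patients.

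**Working it through.** **1. Follow-up windows.** V2 is 2-3 weeks after V1 and V3 is 2-3 weeks after V2, so QLF ends at 4-6 weeks. Reported behaviour runs to 12 months.

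**2. The plan's own figure.** There is none for reported behaviour. The only calculation with an effect size is for plaque percent index: 133 per group, difference 3.5, SD 10, 80% power. With two-sided alpha 0.05 (assumed, since sidedness is not stated) the power is 81.4%, so the statement reproduces. It corresponds to 3.5/10 = 0.35 SD, which serves below as a yardstick.

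**3. Patients lost under each reading.** Let m be the chance of missing any one follow-up occasion, independent across occasions (an assumption, since no rate is given), with V1 complete.

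| Reading | Share lost | m = 10% | m = 20% |
|---|---|---|---|
| Consecutive follow-ups (V2-V3, V3-F1, F1-F2) | 1 - (1 - m)² | 1 - 0.9² = 19% | 1 - 0.8² = 36% |
| Change from V1 to any follow-up | m | 10% | 20% |

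The step V1-V2 loses only m under either reading. Of 133 per arm, change from V1 leaves about 120 or 106. Consecutive pairs leave 133 × 0.81 ≈ 108 or 133 × 0.64 ≈ 85.

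**4. What each reading estimates.** For change from V1, fitting Y_t - Y_1 = a + b·arm + c·Y_1 is the same as fitting Y_t = a + b·arm + (c + 1)·Y_1. The arm coefficient b is identical, and it is the quantity that the QLF model estimates. For consecutive change adjusted for V1, b is the difference between the arm effects at two adjacent occasions, which is a different question.

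**5. Bias at 12 months, change from V1.** Simulation assumptions: 133 per arm, five occasions, equal within-person correlation 0.6, no true effect, higher score better. Drop-out occurs at F1 and F2 with logit -1.75 - slope × last observed score. With slope 1.0 in one arm and 0 in the other, about 67% and 73% are retained at 12 months.

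| Drop-out slopes in the two arms | Complete-pair ANCOVA: bias | Type I error |
|---|---|---|
| 1.0 and 0 | 0.07-0.08 SD | 9-10% |
| 0.5 and 0, or 1.0 and 0.5 | 0.03-0.04 SD | about 6% |
| equal in both arms | none | nominal |

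The ranges cover repeated runs of 3,000 to 4,000 replicates. In the first scenario, correlations of 0.5 and 0.7 gave 0.081 and 0.066 SD. A likelihood estimator using every attended visit (sequential regressions, valid for monotone drop-out) had bias below 0.01 SD there and a slightly smaller standard deviation of the estimate (0.114 against 0.117).

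A simpler three-occasion simulation with a true effect of 0.35 SD and about 26-27% lost at the last visit points the same way. Complete pairs gave 0.40 when drop-out depended on the score in one arm only, and 0.34 when it did so alike in both. The likelihood estimator gave 0.35 in both cases.

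**6. Consecutive change, F1 to F2, first scenario.** Bias is 0.04 SD with 5.9% error when adjusted for F1, and -0.06 SD with 7.7% error when adjusted for V1. Size and sign depend on which reading is used.

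**The case against.** **No exclusion rule is written.** A reader might infer that anyone who misses a visit is dropped from the behaviour analysis. The protocol does not say so. A patient is lost only from the change scores that use the missing visit. Under change from V1, missing V2, V3 or F1 does not affect the 12-month comparison. The telephone calls are planned for all 400 patients, so missing V2 or V3 does not by itself end follow-up. This objection stands and limits the point.

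**Secondary outcome, and the SAP is not shown.** Missing-data detail for such an outcome often sits in the SAP. That is fair for detail. Here, however, the protocol fixes a method for each family of outcomes and gives the weaker one to the longer follow-up. A SAP that followed the text would inherit that choice.

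**FIML already covers 6 and 12 months.** It does for the prediction models. Those relate change in perceived susceptibility to later behaviour, and as placed the sentence does not reach the comparison of information arms.

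**The harm rests on assumptions.** This is correct. The protocol gives no drop-out rate or mechanism. Halving the slope roughly halves the bias, and equal mechanisms with no true effect remove it. The simulations also make drop-out depend on observed scores, the case that favours the mixed model. If people leave because of current, unobserved behaviour, neither method is protected.

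**Cost-benefit results.** A reader might infer that a biased 12-month figure drives net benefit. It does not: net benefit is mean WTP minus mean intervention cost, and the behaviour data only illustrate.

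**Conclusion.** The point holds as an inconsistent and ambiguous choice of method for a secondary outcome. The arm comparison of reported behaviour uses available pairs by construction, with no missing-data method attached, while a better method is already planned a section later for a shorter follow-up.

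Under change from V1 and drop-out that depends on the last score more strongly in one arm, the 12-month bias is about 0.04-0.08 SD, with 6-10% type I error against 5%. Against the 0.35 SD yardstick that is 0.04/0.35 ≈ 11% to 0.08/0.35 ≈ 23%. These figures are illustrations under assumed drop-out and do not predict this trial's results.

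Two stronger conclusions are not supported. One is that the plan will credit an arm with sustained change: for consecutive F1-F2 change the bias is smaller and can reverse sign. The other is that the trial's main result is at risk: WTP is collected at V1 and later drop-out does not touch it.

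**What to change.** In Behaviour change and mediating variables:

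1. Define change as change from V1, and remove the wording that suggests steps between consecutive visits.
2. Compare arms with the repeated-measures mixed model already planned for QLF: reported behaviour at V2, V3, F1 and F2 as outcomes, arm by occasion, V1 behaviour as covariate, and all randomised patients with any follow-up. By step 4 of the working, this keeps the arm estimate that change from V1 with baseline adjustment targets.
3. For items that cannot reasonably be treated as continuous (five- and seven-category responses, tobacco questions), specify an ordinal or binary version of the model.
4. Use the 12-month estimate from this model for the illustration in the cost-benefit framework analysis.
5. Report drop-out by arm at each occasion, so that readers can judge whether a difference in mechanism is plausible.

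The cost is a change of wording and somewhat more modelling work for the categorical items. No new data are needed, and the sample size, the WTP analysis and the net-benefit formula are unchanged. The model does not protect against drop-out driven by unobserved behaviour, and the report should say so.

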## Procedures (see Flow diagram and Study Crib sheet)

# Visit 1 (V1):

Before their dental check-up, for patients recruited to the study a measure of the patients' literacy (REALM) will be administered by a dental nurse. The following data will then be gathered as self-reports: demographic (age, gender, income, education, employment status); psycho-graphic (previous experience of dental care, self-rated oral health, dental anxiety (MDAS); and oral health behaviours (diet, oral hygiene and smoking).

Information on patients' hypothetical incremental Willingness to Pay (WTP) for both the Traffic Light and QLF information systems (using Verbal information only as a base line for comparison), will be gathered. The systems will be explained hypothetically using written and visual information giving a generalised description of that type of information, but without reference to the patients' personal oral health status/risk. Following an outline of the 3 scenarios, patients will first be asked which of the forms of information is preferred including the current practice of Verbal information only (ranking) and then incremental WTP will be elicited for traffic light and QLF both compared to Verbal only (i.e. what extra would some be willing to pay (if at all) to receive either traffic light or QLF over verbal information only) in this face to face setting.

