WTP will be elicited using a shuffled payment card method, where a range of values are shown to the patient one at a time in a random order (Smith, 2006). The participant then decides for each value whether they are willing to pay the amount, unwilling to pay it or unsure. This then leaves a range between the lowest value that the participant is unwilling to pay and the highest value that they are willing to pay. The patient will then be asked to name the value between (and including) these values that would be the maximum they would be willing to pay. The decision for each card therefore is similar to a dichotomous choice (as recommended by Arrow and Solow, 1993)), but the whole process finishes with an open ended question. This approach minimises some of the problems associated with using either one of these methods on their own, such as starting point and range bias and making the cognitive task too difficult. Where participants give a zero value, they will be asked to identify the reason for the zero valuation from a range of options presented verbally and on a card. This will allow zeros to be later classified as true zeros or protest responses.

Baseline QLF photographs will then be taken of all patients to measure plaque levels. The patients will then brush their teeth and a second QLF photograph taken to measure tooth mineralisation. At this stage there will be no disclosure of the photograph to patients.

Patients will then have their dental check-up appointment (which will include a BPE examination). The dentist will open the randomisation envelope and patients will then be given their own personal risk information according to the randomisation schedule: either 1) Verbal only information (Model 1) or 2) Verbal information supported by a printed copy of the patients' oral health and risk of disease displayed as a traffic light (Red, Amber or Green), (Model 2) or 3) Verbal information supported by the QLF photographs taken earlier.

In the QLF arm the dentist will discuss the images with the patient in an electronic form on a Tablet PC. These patients will be offered an e mailed electronic image and/or a printed copy of the most meaningful image (either plaque or mineral loss) in a credit card size. A record will be made if an electronic image is sent. In the Traffic Light arm patients will be given a

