credit-card sized information showing their risk level according to colour on the card. In the Verbal only arm patients will receive a plain card with a checklist where the message given by the dentist is written. The reverse of the credit-card sized information from the QLF arm and the Traffic Light arms will have the same checklist (Figure 1):

Figure 1: Checklist of possible preventive messages given to patients

- Stopping or quitting smoking
- Following your dental treatment plan

Following the check-up the dentist or nurse will record as data variables:

- The number of natural teeth present
- Whether the patient is exempt or not from NHS charges
- Any messages given as checked against the Figure 1 list
- The Red, Amber or Green risk rating assigned to patients in the Traffic Light arm

Following the dental appointment, all patients will be given the opportunity to revise their WTP for the information form experienced (therefore this will not be relevant to those in Model 1 who receive only verbal information and they will not undertake this part of the study). For this re-valuation, patients will be reminded of their initial valuation and then asked in a single open-ended question format if they wish to change the value and what amount they would change to.

Self-report data will then be collected at this point on:

- Intention to behave according to the behaviours listed in Figure 1 before the next appointment
- Behaviour change variables as outlined by the Extended Parallel Process Model (EPPM) (Severity of Threat, Susceptibility of Threat, Self-Efficacy and Response Efficacy). The 'threat' here will be the threat of poor oral health and its consequences identified from Phase 1 (for detail see Measures: 5b Risk (threat) perception). An additional set of items will be added to reflect affect concerned with negative oral health outcomes i.e. '*How would you feel if...*' (in addition to the cognition set reflected in EPPM domains).
- Patient-Clinician communication (Communication Assessment Tool, CAT).

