## Figure 2: Extended Parallel Process Model

If the perceived threat is low, the message will be ignored, efficacy will not be considered and no further action will be taken. However if the perceived threat is high the individual will follow one of two pathways, 'danger control processes or fear control processes' (Witte et al., 2001). If perceived threat and efficacy are both high the individual will follow the danger control pathway and focus on dealing with and solving the problems posed by the threat (Gore, 2005). If perceived threat is high but efficacy is low the individual will follow the fear control pathway. This involved maladaptive coping strategies such as denial, reactance or avoidance (Witte, 1992; 1994; Gore, 2005)

b) Risk (threat) perception:

From the qualitative study, we identified 5 perceived possible negative outcomes of poor oral health likely to be important to participants.

1=If your teeth were to make you feel uncomfortable when smiling, talking and laughing in front of people

2=If people thought you had failed to look after your own teeth

3=If your teeth were to become more painful and sensitive

4=If you were to need treatment which meant spending more time at the dentist

5=If you were to need treatment which you could not afford

Threat suceptibility: To eliminate the confounding effects of intentions to improve behaviour in future, participants will be asked to make conditional estimates of likelihood, "If you do not

follow the dentist's advice, how likely is it that.. [negative outcome..] Estimates are rated on a five-point Likert scale ranging from 1=absolutely unlikely to 5 absolutely likely.

Threat severity: Potential outcome severity is assessed using the question '*How serious* would it be to you if [negative outcome] were to occur, on a five-point Likert scale ranging from 1=not at all serious to 5=absolutely serious.

Self efficacy: will be assessed using a stem question of '*Please consider how confident you are that you can perform the behaviour properly, regularly and on a long term basis*' for each of the 6 target behaviours, using a 5 point Likert response scale from 1=not at all confident to 5=absolutely confident.

Response efficacy: will be assessed using the item format '{target behaviour] *means I am less likely to have dental problems,* using a 5 point Likert response scale from 1=Absolutely disagree to 5=Absolutely agree.

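### The lead predictor of behaviour change, V1-to-V2 change in perceived susceptibility, starts after the information has been given, so it leaves out the immediate response

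*Protocol*

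**What the plan says.** In Phase 2 Analysis, under Behaviour change and mediating variables, the protocol notes that the intervention happens at the first visit and concludes from this that "the change in EPPM scores (susceptibility to risk) from V1 to V2 will be used as the primary predictor variable". It continues: "This will be used to predict changes in oral health behaviour from V2 to V3". The same change score is also to predict behaviour change from V2 to the 6-month and 12-month telephone follow-ups, within structural equation models.

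Two other statements in that section matter. The sentence before this argument names EPPM variables from V1, and partly from V2, as predictors of later behaviour change. A separate analysis compares reported behaviour change between conditions, using follow-up minus baseline with baseline as covariate.

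The order of events is set under Procedures, Visit 1:

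- Before the check-up, the self-reports are demographic, "psycho-graphic (previous experience of dental care, self-rated oral health, dental anxiety (MDAS); and oral health behaviours (diet, oral hygiene and smoking". No EPPM item is listed.
- At the check-up, "patients will then be given their own personal risk information according to the randomisation schedule".
- After it, "Following the dental appointment, all patients will be given the opportunity to revise their WTP for the information form experienced". Then comes "Self-report data will then be collected at this point on" a list that includes "Behaviour change variables as outlined by the Extended Parallel Process Model (EPPM", with susceptibility among its four components.

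Under Visit 2, scheduled 2-3 weeks later, the susceptibility items are repeated before the patient sees the dental team. Measures, item 5, lists no other EPPM measurement.

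**The concern.** Deriving the predictor from the timing of the intervention works only if the V1 score precedes the intervention. It follows it. The quantity called the primary predictor is therefore a difference between two post-information scores and cannot show how far the information moved perceived susceptibility at the time it was given.

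The outcome windows add to this. Behaviour has a true pre-information baseline at V1 and is measured again at V2, but the prediction models count change only from V2 onward. The protocol's own instruments treat the interval to V2 as a period when change is expected: intention and danger-control items ask about the time before the next appointment, and the V2 items ask what the patient has done since the last one.

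At stake is how the mechanistic part of Objective 6 can be read. A null result for this predictor would not show that risk information fails to work through perceived threat. A positive result would link drift in susceptibility after the information to later drift in behaviour.

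**Working it through.** The protocol attaches no figure to this model. Its one power calculation concerns the plaque index and does not enter here. The check is of timing, followed by an illustration on assumed values.

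**1. Order of measurement**

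| Point | Susceptibility | Behaviour |
|---|---|---|
| V1, before check-up | not measured | measured |
| V1, check-up | information given | – |
| V1, after check-up | measured (first time) | intention only |
| V2 (2-3 weeks after V1) | measured (second time) | measured |
| V3 (2-3 weeks after V2) | not measured | measured |
| 6 and 12 months after V1 | not measured | measured |

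The item wording agrees with this order. Susceptibility is asked conditionally on not following the dentist's advice, which presupposes that advice has been given.

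**2. What the change score contains**

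Let P be the unmeasured pre-information level, R the immediate response, k the share of R present at V2, and e1, e2 measurement error.

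- V1 score = P + R + e1
- V2 score = P + kR + e2
- Planned predictor = V2 − V1 = (k − 1)R + e2 − e1

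If the response persists fully (k = 1), the predictor is error alone. Otherwise it reflects R only through what happened after V1. This is algebra and needs no assumed values.

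**3. How much of R it carries (illustration; all values assumed)**

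Take SD of R = 0.5 and error SD = 0.4. With R independent of the errors,

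corr(predictor, R) = (k − 1) × 0.5 / √[(k − 1)² × 0.25 + 2 × 0.16]

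| k | Calculation | Correlation |
|---|---|---|
| 0.5 | −0.25 / √0.3825 | −0.40 |
| 0.8 | −0.10 / √0.33 | −0.17 |
| 1.0 | 0 / √0.32 | 0.00 |
| 1.2 | 0.10 / √0.33 | +0.17 |
| 1.5 | 0.25 / √0.3825 | +0.40 |

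Size and sign are set by k, which the protocol gives no means of knowing. A simulation with the same assumed values for k = 0.5, 0.8 and 1.0 agrees to within 0.01. For comparison, the post-information V1 score, with an assumed SD of P of 1 and P independent of R, correlates with R at 0.5 / √(1 + 0.25 + 0.16) = 0.5 / 1.187 = 0.42, whatever the value of k.

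**4. The outcome window**

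Change V1 to V3 = (change V1 to V2) + (change V2 to V3). The omitted first term covers 2-3 of the 4-6 weeks between V1 and V3. If a share f of the change by V3 has occurred by V2, the V2-to-V3 outcome holds 1 − f of it: 50% for f = 0.5, 30% for f = 0.7 and 0% for f = 1. These values of f are assumptions. The protocol gives none.

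**The case against.** **V1 EPPM scores are already named as predictors.** This stands. The plan as a whole does not lack a predictor that contains the response. The fault lies in which variable is made primary and in the reason given for it.

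**Early behaviour change is analysed elsewhere.** This also stands. The between-condition analysis of reported behaviour uses change from baseline, and the section on comparing clinical outcomes between arms models the V2 and V3 QLF measures with the V1 value as covariate. Only the prediction models start at V2.

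**Starting the outcome at V2 keeps the predictor ahead of the outcome.** This is a sound reason for the window, given a predictor measured over V1 to V2. The window follows from the predictor and is not a second independent error. But temporal order helps only if the predictor carries the response, and a predictor taken at V1 after the information would precede V2 behaviour as well.

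**The change score need not measure fading.** Correct. Patients in every arm take a card home, and QLF patients are offered an emailed image, so susceptibility may rise, fall or stay level. A delayed effect would fall in the planned windows. What is lost is the immediate response.

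**Stronger readings that a reader might infer:**

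- That a susceptibility predictor contradicts the theory, because "If perceived threat is high but efficacy is low the individual will follow the fear control pathway". The text says primary predictor within structural equation models. It does not exclude efficacy or interactions, efficacy is collected, and path details may be left to a statistical analysis plan.
- That a mean fall in susceptibility after V1 would reverse the sign of the estimated association. A regression slope depends on covariance between patients, not on the sign of a mean change, and the document supplies no values for either.

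**Conclusion.** The concern holds for the predictor and, as a consequence, for the windows of the prediction models. The reason stated for the primary predictor is contradicted by the protocol's own Visit 1 schedule. The V1-to-V2 change excludes the immediate response, and the models' outcomes omit behaviour change in the first 2-3 weeks. That rests on the documented order of events alone. The correlations and percentages in the working rest on assumed values and show only how strongly the reading depends on them.

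The reach is limited. This is the mechanistic part of Objective 6, under what Measures, item 5, calls a secondary aim. It would be wrong to infer that Objective 6 cannot be answered or that the trial misses the effect of the information: arm differences in behaviour and QLF outcomes are estimated from a proper baseline, and the willingness-to-pay primary outcome does not use this predictor. The correction is worth making because it is cheap and changes what the lead mechanistic result would mean.

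**What to change.** Amend Behaviour change and mediating variables as follows, using only data already scheduled:

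1. Make the post-information V1 EPPM scores the lead predictor or mediator, with randomised arm as the exogenous variable. Delete the inference from the timing of the intervention to the V1-to-V2 change.
2. Define behaviour change in these models from the pre-check-up V1 baseline to V2, V3, 6 months and 12 months, with baseline behaviour as covariate.
3. Keep the V1-to-V2 susceptibility change as a secondary variable, labelled persistence after the information, and use it only for outcomes after V2.

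No new pre-check-up items are needed. The susceptibility question is conditional on advice already given, so a reworded earlier version would be a different item and would not yield a clean within-patient change.

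The cost is a wording change. The statistical price is that the mediator is compared across arms rather than as a change within each patient, and the V1 score carries patients' differing pre-information levels as well as their response. Since every arm receives verbal information, the contrast is between forms of information, not information against none. That is the contrast Objective 6 asks about.
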